Statistical Analysis	As treated analysis will be performed with mean, t-tests, within and between group ANOVA, linear regression, Mann- Whitney-Wilcoxon tests

CONFIDENTIAL

This material is the property of the NYU School of Medicine and Langone Medical Center. Do not disclose or use except as authorized in writing by the study sponsor
Interventional Template Version: 28 APR 2017

1 Key Roles

PI: [name]
Department of Orthopedic Surgery and Cell Biology
NYU Langone Medical Center
[name]
[contact]
[contact]

Co-PI:

[name]
Assistant Professor of Anesthesiology
NYU Langone Orthopedic Hospital
NYU Langone Health
[name]
[name]
[contact]

2 Background and Specific Aims

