administration which showed a statistically significant difference in pain scores and narcotic usage administration between the two groups on post-operative day one, with those who received SSI having less pain and narcotic usage. What remains to be seen is how these interventions impact rehabilitation and narcotic usage in the long-term.

After sustaining hip or other lower extremity fractures, roughly 50% of patients experience persistent pain at the fracture site. Their perception of this pain and the limitations that they suffer because of it may be influenced by their perioperative pain control and expectations regarding their pain and ability to return to normal living⁶. The goal of this study is to not only impact the acute use of narcotics during the inpatient admission but to impact the long term outcome of fracture pain on long-term functional outcomes for these patients.

At our institution pre-op fracture pain management was not standardized and had been a combination of morphine, fentanyl, dilaudid, and oxycodone given in the emergency and in-patient setting. Post-operatively, oxycodone-acetaminophen 5-325mg and 10-325mg were given for moderate and severe pain every four hours respectively with a dose of oxycodone-acetaminophen 5-325 for breakthrough pain. Adjuncts to these medications such as acetaminophen, tramadol, ketorolac, ofirmev, gabapentin, pregabalin were given inconsistently and often not at all. Starting November 2018 our institution began a new post-op pain medication protocol. In this study a standardized regimen of pain medication will be given to all patients who are enrolled to eliminate this as a potential confounder. The ultimate goal of this study is to diminish the use of post-op narcotics and reduce post-operative pain through the use of an intra-operative SSI.

Rationale for Drug Selection and Route of Administration

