2.2 Specific Aims

AIM 1: To determine if SSI given to during lower extremity fracture surgery reduces post-operative pain. This will be evaluated through the randomizing patients who either receive general or spinal anesthesia into two separate groups, injection or control, and monitoring their pain scores afterwards both in the hospital and outpatient settings. (The type of anesthesia will be determined by the treating anesthesiologist; it is not an experimental variable.)

AIM 2: To determine if SSI given during lower extremity fracture surgery significantly changes post-operative narcotic usage. Using the same groups as above, this will be evaluated through the measurement of narcotic usage both in the immediate post-operative period and for 2 weeks after surgery.

AIM 3: To determine if SSI given during lower extremity fracture surgery alters post-operative function, length of stay, and complications after surgery. This will be measured through rehabilitation documentation, discharge documentation, chart review, and patient interviews.

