2.4 Objectives and Purpose

The ultimate goal of this study is to determine how effective SSI is in reducing post-operative pain in patients with lower extremity long bone fractures and to determine how that reduction in post-operative pain impacts a patient's hospital stay in the short term and their use of narcotics during the treatment period. Primary outcomes measures will be reported and observed pain scores and narcotic use. VAS and APS-POQ will be used to measure pain scores. While it is expected that the greatest benefit of the SSI will be seen in the first day or two after surgery it is possible that there will be an overall reduction in long-term narcotic use. Secondarily, function/rehabilitation, length of stay, and complications may be impacted by the intervention.

CONFIDENTIAL

This material is the property of the NYU School of Medicine and Langone Medical Center. Do not disclose or use except as authorized in writing by the study sponsor

Interventional Template Version: 28 APR 2017

3 Study Design and Endpoints

Cohort A: Spinal Anesthesia	ARM 1: Experimental	Sample Size: 100	SSI
	ARM 2: Control	Sample Size: 100	No intervention

Cohort B: General Anesthesia	ARM 1: Experimental	Sample Size: 100	SSI
	ARM 2: Control	Sample Size: 100	No intervention

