Physical therapy records with regards to ambulation distance and exercise endurance will be examined. Daily assessments of pain via VAS will be obtained by the nursing staff as per standard protocol. APS-POQ form will be given on POD1.

After discharge subjects will receive a 7-10 day prescription for acetaminophen 1000mg every 8 hours, meloxicam 15mg oral once daily, and tramadol 50mg oral, every 4-6 hours, PRN (12 tablets to be dispensed). Subjects will call the provider to request refills as needed.

CONFIDENTIAL

This material is the property of the NYU School of Medicine and Langone Medical Center. Do not disclose or use except as authorized in writing by the study sponsor

Interventional Template Version: 28 APR 2017

[figure not shown]
After discharge the research staff will call the subjects up to every other day for the first week, twice in the second week, once weekly for the third and 4th weeks and then monthly after discharge to ascertain pain level, reported narcotic usage, and functional status. Research staff will verify documented narcotic refills through epic and pharmacy records. Four to eight weeks after injury subjects will complete a SMFA as well as another APS-POQ form over the phone with a trained interviewer.

	Pre-op	Post-op: Inpatient	Post-op: Discharge
Standing	Acetaminophen 1gm, oral (every 6-8 hours, not to exceed 4gm daily, review liver function prior to administration)	Acetaminophen 1gm, oral (every 6-8 hours, not to exceed 4gm daily, review liver function prior to administration)	Acetaminophen 1gm, oral (every 6-8 hours, not to exceed 4gm daily, review liver function prior to administration)
	Meloxicam 15mg oral, once daily	Ketorolac 30mg inj, once daily in AM, starting POD1 (15mg>65 years of age and/or renal impairment) Pregabalin (Lyrica) 50mg, oral every 8 hours (hold for sedation)	Meloxicam 15mg oral, once daily
Mild		Ice Therapy PRN (alternating 15 min on/off for skin evaluation)	
Moderate		Tramadol 50mg oral, every 8 hours, PRN	
Severe		Tramadol 100mg, oral, every 8 hours, PRN	
Breakthrough		Oxycodone 5mg, oral every 6 hours, PRN	Tramadol 50mg oral, every 4-6 hours, PRN (12 tablets to be dispensed)

CONFIDENTIAL

This material is the property of the NYU School of Medicine and Langone Medical Center. Do not disclose or use except as authorized in writing by the study sponsor
Interventional Template Version: 28 APR 2017

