6.2 Analysis of Endpoints

Primary Endpoints:

amount (mg) of narcotics (oral morphine mg equivalents) used
duration of narcotic use
patient reported pain scores

Secondary Endpoints:

length of stay
progress with physical therapy: distance ambulated, range of motion, exercises done
reported long-term narcotic use at home/SAR
discharge location: home, acute rehab, skilled nursing facility
documented narcotic refills
falls
adverse events

The analysis of narcotic Use, VAS, APS-POQ, and SMFA scores will rely on a univariate repeated-measures analysis of variance model for mean score. This model is in the class of models commonly known as a unirep-ANOVA models. It assumes that the mean score is a function of elapsed time and the treatment regimen assigned. This model takes into account the fact that the subject's repeated measures are correlated. The fitted model will provide statistical estimates of the mean levels, the treatment-effect differences between mean levels, the standard deviation, the intra-class correlation coefficient, 95% CIs, standard errors (SE), and statistical hypothesis tests. The estimates of means will be used to compute summary criteria such as area under the curve (AUC) for each regimen. All estimates reported will be presented their 95% CIs.

CONFIDENTIAL

This material is the property of the NYU School of Medicine and Langone Medical Center. Do not disclose or use except as authorized in writing by the study sponsor

Interventional Template Version: 28 APR 2017

All endpoints will be evaluated as fits the data set with graphical figures such as scatter plots, box-and-whisker plots, and frequency histograms to visualize the distribution of these outcomes and their relationships to covariates and treatment assignment. When appropriate descriptive graphical and tabular methods, and Kaplan-Meier curves will also be estimated and presented in a graphical figure.

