6.3 Sample Size

In order to have a sufficient N to power the study a minimum of 200 subjects per anesthesia group will be recruited ($\alpha=0.05$, $\beta=0.2$). If the difference in the morphine equivalent consumption, is found to be 15mg daily with a standard deviation between the groups of 25mg, we will need 90 subjects per group in order to reject the null hypothesis with the probability (power) 0.8. The Type I error probability associated with this test of this null hypothesis is 0.05. To allow for within group analyses and accommodate for the poor follow-up rate in fracture patients we will need 400 patients.

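### Section 6.2 states no arm-by-time term or main time window although benefit is expected in the first two days, and it leaves out the anaesthesia stratum and pre-operative VAS

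*Combined protocol and SAP*

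**What the plan says.** Section 6.2 applies one univariate repeated-measures ANOVA to narcotic use, VAS, APS-POQ and SMFA. Its mean structure is given in one sentence: "It assumes that the mean score is a function of elapsed time and the treatment regimen assigned". It adds that "The estimates of means will be used to compute summary criteria such as area under the curve (AUC) for each regimen", with no window for that area. The Protocol Summary lists "within and between group ANOVA" among the methods, again with no terms or time points. Covariates appear in 6.2 only in connection with graphs, and none is named.

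On timing, section 2.4 says "it is expected that the greatest benefit of the SSI will be seen in the first day or two after surgery", and section 2.1 reports that the cited femur-fracture trial found a "statistically significant difference in pain scores and narcotic usage administration between the two groups on post-operative day one". Aim 2 in section 2.2 calls for "measurement of narcotic usage both in the immediate post-operative period and for 2 weeks after surgery". After discharge, section 3.1 schedules calls "up to every other day for the first week, twice in the second week, once weekly for the third and 4th weeks", and monthly thereafter.

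Section 6.4 randomises within general or spinal anaesthesia. Section 3.1 enrols patients before surgery and has nursing staff score VAS every four hours from recruitment, so pre-operative values will exist. Section 6.3 bases the sample size on a difference of "15mg daily with a standard deviation between the groups of 25mg" and attaches no day to either figure.

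**The concern.** The plan expects its largest effect in a short early window but measures for weeks, and it does not say which comparison over time tests the arms. If the arm main effect over all times is used, a difference on the first two days is averaged with later days that may show little or none. If an arm-by-time test or a day-specific difference is used, it is not. The same data could give opposite answers, and the choice is open until the data are seen.

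Three smaller matters concern the same model. A pooled analysis that ignores the randomisation stratum has wider intervals than necessary. A VAS analysis that ignores the pre-operative score gives up precision, and because the start of elapsed time is undefined, pre-treatment scores could enter the treatment model. Post-discharge times are unequally spaced, and no covariance structure or sphericity correction is named.

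**Working it through.** **The plan's own figure.** With a 15 mg difference, SD 25 mg, two-sided 0.05 (sidedness is not stated, so this is assumed) and power 0.80, the exact t-test needs 45 per arm, or 90 in two arms. The 90 in section 6.3 therefore reproduces as the total within one anaesthesia cohort; 90 per arm would give 98% power. It is a single-comparison calculation, so it does not settle which time window is meant.

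**Dilution of an averaged arm effect.** From the plan: 15 mg/day, SD 25 mg (variance 625), and 100 per arm in one cohort (section 3). Assumed: the effect is present on the first 2 of T equally weighted occasions and zero after, with equal within-patient correlation ρ of 0.3, 0.5 or 0.7.

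- Average difference: Δ = 2 × 15 / T
- SE = √{2 × 625 × [1 + (T − 1)ρ] / (T × n)}
- Power from the noncentral t, 2n − 2 degrees of freedom, two-sided 0.05

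Example, T = 7, ρ = 0.5, n = 100: Δ = 4.29 and SE = √(1250 × 4 / 700) = 2.67, so power is 36%.

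| Averaging, n = 100 | Δ (mg/day) | ρ = 0.3 | 0.5 | 0.7 |
|---|---|---|---|---|
| Days 1-2 | 15.00 | >99% | >99% | >99% |
| 7 days, or 7 occasions in 2 weeks | 4.29 | 48% | 36% | 29% |
| 8 occasions in 2 weeks | 3.75 | 40% | 29% | 23% |
| 14 daily values | 2.14 | 17% | 13% | 11% |

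The 7- and 8-occasion rows use assumed schedules closer to the calls in section 3.1: days 1, 2, 3, 5, 7, 10, 14, or days 1, 2, 3, 5, 7, 9, 11, 14.

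**Other sample sizes.** Section 4.6 expects 300-350 evaluable. At 75 per arm (300/4), power is 98-99% over 2 days, 23-38% over 7 and 9-14% over 14. Pooled at 150 per arm (300/2), it is above 99%, 40-65% and 14-24%.

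**Relaxing the assumptions (n = 100, same ρ range).**
- An assumed 5 mg/day persists after day 2. Over 14 days Δ = (2 × 15 + 12 × 5)/14 = 6.43, power 57-86%; over 7 days Δ = (2 × 15 + 5 × 5)/7 = 7.86, power 73-94%.
- The SD after day 2 is an assumed 8-15 mg and the late effect is zero. The variance of a patient's mean is [ρ(Σσ)² + (1 − ρ)Σσ²]/T². For T = 14, σ = 15 after day 2 and ρ = 0.5, this is (0.5 × 230² + 0.5 × 3950)/196 = 145.0, so SE = √(2 × 145.0/100) = 1.70 and power is 24%. Over the whole range, power is 19-67% at 14 days and 50-94% at 7 days.
- An omnibus arm-by-time F test for the two-day effect, under equal correlation and constant SD 25 mg, has power above 99.8% at both T = 7 and T = 14.

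**Stratum left out of a pooled model.** Assume a gap of 10-25 mg between anaesthesia cohorts. Variance ratio = 1 + (gap²/4)/625 = 1.04 to 1.25, so intervals are √1.04 = 1.02 to √1.25 = 1.12 times as wide. True type I error = 2[1 − Φ(1.96√ratio)] = 4.6% to 2.8%.

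**Pre-operative VAS left out.** Adjustment narrows intervals by 1 − √(1 − r²), which is 5% at an assumed r = 0.3 and 13% at r = 0.5.

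**Sphericity.** On the two schedules above, with an assumed correlation of 0.5-0.9 per day of separation and 300 patients, simulation of an uncorrected arm-by-time test gave about 6-10% rejection under no effect.

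**The case against.** The strongest reply is that section 6.2 never says the model is additive. A mean that depends on time and regimen can include their interaction. The AUC by regimen and the within- and between-group ANOVA suit that reading, and under it the early effect is not diluted. This stands: a reader might infer that the model cannot see an early effect, and the documents do not support that. What remains is that no contrast is designated.

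A reader might also take 11-17% as the trial's power. It is not. It needs 14 equally weighted daily values, no effect after day 2 and a flat SD of 25 mg. Section 3.1 does not provide daily values after discharge. Late consumption may also vary less: the discharge supply is 12 × 50 mg = 600 mg tramadol, which the two tables in section 14.1 convert to 60 mg (factor 0.1) or 150 mg (10/40). That is about 6-21 mg/day over 7-10 days, before refills. The calculation covers narcotic use only. VAS is scored every four hours in hospital, so an average over recorded VAS occasions would weight the early period far more heavily.

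Next, sections 2.2 and 2.3 also aim at outpatient effects, and section 2.4 speaks of the greatest benefit, not the only one. Making POD1-2 the sole main contrast would be partly a preference. That also stands, and the fix allows for it.

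Finally, the stratum needs no term if the cohorts are analysed separately, as the per-cohort sample sizes in sections 3 and 6.3 suggest. The plan does not say which analysis applies.

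**Conclusion.** The point holds as a gap in pre-specification. Section 6.2 states neither an arm-by-time term nor a main time window, and the protocol's own expectation of an early effect makes that choice consequential. For a two-day effect at 100 per arm, power is above 99% for a days 1-2 contrast. For averages over 7 days up to two weeks it is roughly 11-48% at constant SD, and higher if the effect persists or late variability is smaller. These figures rest on assumed effect duration, correlation and late SD; only the 15 mg, the 25 mg and the sample sizes come from the plan.

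The omitted stratum and pre-operative VAS are smaller matters. A reader might infer bias or an inflated error rate from them, but neither follows: leaving out the stratum makes a pooled test conservative, and leaving out the pre-operative VAS costs precision only. Inflation to about 6-10% arises only for an uncorrected arm-by-time test under the assumed correlations. The change should be made, but nothing here shows that the trial would fail.

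**What to change.** - **VAS and narcotic use:** fit arm, time and arm-by-time, with modelled time starting after surgery. Pre-specify the POD1-2 arm difference as the first contrast and the two-week or later-period contrast next. If the two-week average is to be the main contrast, say so and state its power.
- **Stratum:** include anaesthesia cohort in any pooled model, or state that the cohorts are analysed separately.
- **Baseline:** include the last pre-operative VAS in the VAS model.
- **APS-POQ and SMFA:** compare APS-POQ by arm at POD1 and at 4-8 weeks, its only two scheduled times. Compare SMFA by arm at its single time.
- **Minor:** for any arm-by-time test, use a Greenhouse-Geisser correction or a covariance suited to unequal spacing.

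The cost is a few sentences of SAP text and slightly more analysis work, with no new visits, data or patients. One limit should be written in: narcotic use after discharge comes from calls made at most every other day, so late-period contrasts must use reported totals, not daily values.

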6.2.1 Baseline Descriptive Statistics

The following patient data will be recorded: age, gender, height, weight, date of admission, date of discharge, injury time, injury type, laterality, surgical approach, implants used, duration of surgery, time to union, contamination, ASA, comorbidities (smoking, cardiac history, diabetes, etc.), CBC (WBC, PCV, HGB, RBC, indices, platelet count, differential), and medications.

6.3 Sample Size

In order to have a sufficient N to power the study a minimum of 200 subjects per anesthesia group will be recruited ($\alpha=0.05$, $\beta=0.2$). If the difference in the morphine equivalent consumption, is found to be 15mg daily with a standard deviation between the groups of 25mg, we will need 90 subjects per group in order to reject the null hypothesis with the probability (power) 0.8. The Type I error probability associated with this test of this null hypothesis is 0.05. To allow for within group analyses and accommodate for the poor follow-up rate in fracture patients we will need 400 patients.

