6.4 Enrollment/Randomization/Masking Procedures

As per standard of care, an anesthesiologist will determine if subjects receive general or spinal anesthesia. Within these groups subjects will randomized to receive a SSI or no intervention. Randomization will be done via redcapautomated computer randomization. After randomization the surgical team will be informed which group the patient has been randomized into.

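### The trial is sized and randomised within anaesthesia type, but the planned model has no anaesthesia term, no arm-by-anaesthesia interaction and no rule for combining or comparing the two cohorts

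*Combined protocol and SAP*

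**What the plan says.** The table opening Section 3 (Study Design and Endpoints) splits the trial by anaesthetic. "Cohort A: Spinal Anesthesia" has 100 experimental and 100 control participants, and the general anaesthesia cohort has the same. In Section 6.4 the anaesthesiologist chooses the type of anaesthesia, and then "Within these groups subjects will randomized to receive a SSI or no intervention". Section 2.2 says of anaesthesia type that "it is not an experimental variable".

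Section 6.3 asks for at least 200 subjects per anaesthesia group. Its calculation rests on this premise: "If the difference in the morphine equivalent consumption, is found to be 15mg daily", "with a standard deviation between the groups of 25mg". It arrives at 90 per group "in order to reject the null hypothesis with the probability (power) 0.8". On error it says: "The Type I error probability associated with this test of this null hypothesis is 0.05". It then goes up to the full total: "To allow for within group analyses and accommodate for the poor follow-up rate in fracture patients we will need 400 patients".

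The repeated-measures model in Section 6.2 makes the mean depend on elapsed time and assigned treatment. It has no term for anaesthesia type and no arm-by-anaesthesia term. The Statistical Analysis row of the Protocol Summary lists within- and between-group ANOVA without naming an interaction. The only subgroup analysis named anywhere is for the reduced ketorolac dose (3.1).

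**The concern.** Anaesthesia type shapes the sample size and the randomisation but is absent from the analysis. Two things follow.

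First, a factor used to stratify randomisation belongs in the model. If pain or narcotic use differs between spinal and general patients, leaving the factor out puts that difference into the residual and widens the interval for the treatment effect. The documents give no figure from which to size this.

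Second, with no stated rule, the within-group analyses in 6.3 leave room for testing the injection separately in each cohort. If one test is significant and the other is not, the natural reading is that the injection works under one anaesthetic only. Two p-values falling on opposite sides of 0.05 do not test that. The result could be a false claim of a differential effect, or a false negative for one cohort.

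**Working it through.** **Inputs.** Alpha 0.05, power 0.80, difference 15 mg/day and SD 25 mg (6.3). Planned cell size 100 per arm per cohort (Section 3). Evaluable total 300-350 of 400 (4.6), which if spread evenly is 300/4 = 75 to 350/4 = 87.5 per arm per cohort (87 used). Alternative effect 10 mg/day (Endpoint row of the Protocol Summary).

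**Assumptions.** The test is two-sided (6.3 does not say), 25 mg is the per-arm SD, the cohorts are equal in size, and each cohort is analysed by a t-test on a single measure.

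**1. The plan's own figure.** n per arm = 2 × (1.96 + 0.84)² × 25²/15² = 43.6, so 44. The t-test gives 44.6, so 45 per arm and 2 × 45 = 90 for both arms. The stated 90 is therefore reproduced if 'group' means one anaesthesia cohort, as it does earlier in the same paragraph. It is not reproduced as 90 per arm, which would have 98% power. Multiplying 25 mg by √2 gives 88 per arm, which is also close, so the arithmetic alone does not settle what 'group' means.

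**2. Separate tests with the same true effect in both cohorts.** Power p in one cohort comes from the noncentral t with noncentrality δ/(25√(2/n)). The chance that exactly one cohort is significant is 2p(1 − p).

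| True effect | n per arm per cohort | Power p | Exactly one significant |
|---|---|---|---|
| 15 mg | 100 | 98.8% | 2% |
| 15 mg | 87 | 97.6% | 5% |
| 15 mg | 75 | 95.5% | 9% |
| 15 mg | 45 (calculated minimum) | 80.4% | 32% |
| 10 mg | 100 | 80.4% | 32% |
| 10 mg | 87 | 74.7% | 38% |
| 10 mg | 75 | 68.2% | 43% |

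For example, at 10 mg and 75 per arm: 2 × 0.682 × 0.318 = 0.434.

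**3. Unequal cohorts.** The split is not controlled, because anaesthesia is not assigned. With an illustrative 150 per arm in one cohort and 50 in the other, exactly one is significant in about 16% of trials at 15 mg and 49% at 10 mg.

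**4. One comparison across both cohorts.** With 150 to 200 per arm in all, power at 10 mg is 93% to 98%, against 68-80% within a single cohort.

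**5. The interaction.** The difference between the two cohort effects involves four cell means, so SE = 25 × √(4/n). This is 5.8 mg at n = 75, 5.4 mg at 87 and 5.0 mg at 100. Multiplying by 2.80 gives the difference detectable with 80% power: 16.2, 15.0 and 14.0 mg. Power for a 10 mg difference between cohort effects is 41-52%, and for a 5 mg difference 14-17%.

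**The case against.** No section says that the injection will be tested separately in each cohort. 'Group' means arm in Aim 1 of Section 2.2, and a within-group ANOVA can mean change over time within an arm. Read literally, the 6.2 model is already a single pooled treatment comparison. No aim or hypothesis claims a different effect by anaesthetic, and 2.2 says anaesthesia is not under study. At the plan's own 15 mg, each cohort has about 95-99% power if 75-100 per arm are evaluable, so discordant results would be uncommon. The 10 mg figure is not described as an expected difference between arms.

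Most of this stands. Separate testing is an inference. It draws support from the per-cohort sizing in 6.3 and from 6.4, where the groups are the anaesthesia groups, but it is not established. It would also be wrong to say that the plan lacks any pooled comparison. What it lacks is one that uses the stratification factor and is named as the answer. The 10 mg figure is the protocol's own, and with SD 25 it needs 99 per arm, close to the 100 planned, but that does not show it was the intended design effect.

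Two points remain. The model omits the factor used for randomisation, and nothing says how cohort results would be combined or compared.

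**Conclusion.** The gap is real and inexpensive to close, and it should be closed. Its consequence depends on the true effect. If the cohorts are tested separately and the effect is common to both, exactly one is significant in about 2-9% of trials at 15 mg with 75-100 per arm per cohort. The figure is about 32-43% at 10 mg, and about 32% at 15 mg if only 45 per arm per cohort are evaluable. These percentages are illustrative, since 6.2 plans repeated measures and the meaning of the 25 mg SD is not clear. Uneven cohorts would raise them.

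A reader might infer that chance alone will often make the injection look effective under one anaesthetic only. The documents do not support that without the condition above, because at the sizing effect and planned numbers it is uncommon. A reader might also infer that the anaesthesiologist's choice biases the comparison of arms within a cohort. It does not, because randomisation is within anaesthesia type. That choice only limits how a difference between the cohorts could be explained.

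**What to change.** **Section 6.2.** Add anaesthesia type to the model. Name as primary the single treatment comparison across both cohorts, stratified by anaesthesia. Assess any difference between cohorts only through the arm-by-anaesthesia interaction, reported with its 95% CI. Show cohort estimates with CIs descriptively and attach no separate significance claims to them.

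**Section 6.3.** Define 'group'. Replace the appeal to within-group analyses with the precision of the interaction: SE 5.0-5.8 mg, with 80% power only for differences of about 14-16 mg between cohort effects. State that a non-significant interaction does not show that the effects are equal.

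**Cost.** Wording only, with no added participants or data. The sponsor gives up stand-alone significance claims for spinal or general anaesthesia and, if the true effect is near 10 mg, gains power for the main comparison.
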